### **5.2.1 Dose Calculations**

Premedications should not be routinely administered prior to dosing of study drugs. See Section 4.5.6 for subsequent premedication recommendations following a nivolumab or ipilimumab-related infusion reaction.

The dosing calculations should be based on body weight. If the subject's weight on the day of dosing differs by > 10% from the weight used to calculate the dose, the dose must be

recalculated. All doses should be rounded up to the nearest milligram per institutional standard. There will be no dose modifications allowed.

### **5.2.2 Dose Delay Criteria**

Dose reductions or dose escalations are not permitted.

Dose delay criteria apply for all drug-related adverse events (regardless of whether or not the event is attributed to nivolumab, ipilimumab, or both). All study drugs must be delayed until treatment can resume (see [Section 4.3.4.](#))

Nivolumab and ipilimumab administration should be delayed for the following:

During Induction, subjects may be dosed no less than 19 days between doses. If dosing is delayed, both nivolumab and ipilimumab must be delayed together. If dosing is resumed after a delay, both nivolumab and ipilimumab must be resumed on the same day.

During Maintenance, subjects may be dosed no less than 24 days between doses. Subjects may be dosed up to 3 days after the scheduled date if necessary. Subsequent dosing should be based on the actual date of administration of the previous dose of drug.

### **Criteria to Resume Treatment**

Subjects may resume treatment with study drug when the drug-related AE(s) resolve to Grade  $\leq$  1 or baseline value, with the following exceptions:

- Subjects may resume treatment in the presence of Grade 2 fatigue
- Subjects who have not experienced a Grade 3 drug-related skin AE may resume treatment in the presence of Grade 2 skin toxicity
- Subjects with baseline Grade 1 AST/ALT or total bilirubin who require dose delays for reasons other than a 2-grade shift in AST/ALT or total bilirubin may resume treatment in the presence of Grade 2 AST/ALT OR total bilirubin
- Subjects with combined Grade 2 AST/ALT AND total bilirubin values meeting discontinuation parameters (Section 4.3.5) should have treatment permanently discontinued
- Drug-related pulmonary toxicity, diarrhea, or colitis, must have resolved to baseline before treatment is resumed
- Drug-related endocrinopathies adequately controlled with only physiologic hormone replacement may resume treatment

If the criteria to resume treatment are met, the subject should restart treatment at the next scheduled timepoint per protocol. However, if the treatment is delayed past the next scheduled timepoint per protocol, the next scheduled timepoint will be delayed until dosing resumes. If treatment is delayed > 6 weeks, the subject must be permanently discontinued from study therapy, except as specified in Section 5.2.3.

### **5.2.3 Discontinuation of Study Therapy**

Subjects **MUST** be discontinued from study therapy **AND** withdrawn from the study for the following reasons:

- Any Grade 2 drug-related uveitis or eye pain or blurred vision that does not respond to topical therapy and does not improve to Grade 1 severity within the re-treatment period **OR** requires systemic treatment
- Any Grade 3 non-skin, drug-related adverse event lasting > 7 days, with the following exceptions for drug-related laboratory abnormalities, uveitis, pneumonitis, bronchospasm, diarrhea, colitis, neurologic toxicity, hypersensitivity reactions, and infusion reactions:
  - Grade 3 drug-related uveitis, pneumonitis, bronchospasm, diarrhea, colitis, neurologic toxicity, hypersensitivity reaction, or infusion reaction of any duration requires discontinuation
  - Grade 3 drug-related laboratory abnormalities do not require treatment discontinuation except:
    - Grade 3 drug-related thrombocytopenia > 7 days or associated with bleeding requires discontinuation
    - Any drug-related liver function test (LFT) abnormality that meets the following criteria require discontinuation:
      - AST or ALT > 8 x ULN
      - Total bilirubin > 5 x ULN
      - Concurrent AST or ALT > 3 x ULN and total bilirubin > 2 x ULN
- Any Grade 4 drug-related adverse event or laboratory abnormality, except for the following events which do not require discontinuation:
  - Grade 4 amylase or lipase abnormalities that are not associated with symptoms or clinical manifestations of pancreatitis. It is recommended to consult with the BMS Medical Monitor for Grade 4 amylase or lipase abnormalities.

□ Isolated Grade 4 electrolyte imbalances/abnormalities that are not associated with clinical sequelae and are corrected with supplementation/appropriate management within 72 hours of their onset

□ Any dosing interruption lasting > 6 weeks with the following exceptions:

□ Dosing interruptions to allow for prolonged steroid tapers to manage drug-related adverse events are allowed. Prior to re-initiating treatment in a subject with a dosing interruption lasting > 6 weeks, the PI will discuss feasibility with the sponsor.. Tumor assessments should continue as per protocol even if dosing is interrupted.

□ Dosing interruptions > 6 weeks that occur for non-drug-related reasons may be allowed if approved by the BMS medical monitor. Prior to re-initiating treatment in a subject with a dosing interruption lasting > 6 weeks, the BMS medical monitor must be consulted. Tumor assessments should continue as per protocol even if dosing is interrupted.

□ Any adverse event, laboratory abnormality, or intercurrent illness which, in the judgment of the Investigator, presents a substantial clinical risk to the subject with continued nivolumab or ipilimumab dosing.

- Withdrawal of informed consent (subject's decision to withdraw for any reason).
- Any clinical adverse event, laboratory abnormality or intercurrent illness which, in the opinion of the investigator, indicates that continued treatment with study therapy is not in the best interest of the subject.
- Pregnancy
  - All WOCBP should be instructed to contact the investigator immediately if they suspect they might be pregnant (e.g., missed or late menstrual period) at any time during study participation. Institutional policy and local regulations should determine the frequency of on study pregnancy tests for WOCBP enrolled in the study.
  - The investigator must immediately notify BMS in the event of a confirmed pregnancy in a patient participating in the study.
- Termination of the study by Bristol-Myers Squibb (BMS).
- Imprisonment or the compulsory detention for treatment of either a psychiatric or physical (e.g., infectious disease) illness.

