
Criteria for Evaluation: (Efficacy, safety, stopping rules, etc.)
	
Efficacy will be evaluated at week 12 and then every 12 weeks until progression or treatment discontinuation.
 
Safety will be assessed at every treatment visit.

Statistics:
	
A single-stage trial design will be employed.
 
 
• Type I error rate of 5%, power of 80%
 
• Null hypothesis of 5% response rate
 
• Alternate hypothesis of 20% response rate
 
• Response will be defined as those patients who achieve RECIST CR + PR.
 
• Accounting for attrition (inevaluable patients, 25%) and screen fails (5%), up to 39 patients are needed to achieve a target enrollment of 27 evaluable patients.
 

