## **Nivolumab Combined with Ipilimumab**

In the Phase 1 study CA209004, ascending doses of nivolumab have been studied concomitantly with ascending doses of ipilimumab in subjects with unresectable or metastatic melanoma. In each arm in this multi-arm study, ipilimumab was administered once every 3 weeks for 4 doses with nivolumab administered once every 3 weeks for 8 doses. Starting at week 24, ipilimumab and nivolumab were administered once every 12 weeks for 8 doses. The three initial dose-escalation cohorts consisted of Cohort 1 (nivolumab 0.3 mg/kg plus ipilimumab 3 mg/kg; n=14), Cohort 2 (nivolumab 1.0 mg/kg plus ipilimumab 3 mg/kg; n=17) and Cohort 3 (nivolumab 3.0 mg/kg plus ipilimumab 3 mg/kg; n=6). Later, the study was amended to include Cohort 2a which evaluated nivolumab 3 mg/kg plus ipilimumab 1 mg/kg (n=16). The following DLTs were observed in Cohort 1 - Grade 3 elevated AST/ALT (1 subject); in Cohort 2 - Grade 3 uveitis (1 subject) and Grade 3 elevated AST/ALT (1 subject) and in Cohort 3 - Grade 4 elevated lipase (2 subjects) and Grade 3 elevated lipase (1 subject). Based on these data, Cohort 2 was identified as the maximum tolerated dose (MTD) and Cohort 3 exceeded the MTD.

As of 15-Feb-2013, a total of 53 melanoma subjects were treated with nivolumab combined with ipilimumab in CA209004 across cohorts 1, 2, 2a, and 3. At least one AE regardless of causality has been reported in 98% of subjects treated. The most common (reported at > 10% incidence) treatment related AEs (any Grade %; Grade 3-4 %: 93; 53) are rash (55; 4), pruritus (47; 0), vitiligo (11; 0), fatigue (38; 0), pyrexia (21, 0), diarrhea (34; 6), nausea (21, 0), vomiting (11, 2), ALT increased (21; 11), AST increased (21; 13), lipase increased (19; 13), amylase increased (15, 6), headache (11, 0), and cough (13, 0).

The majority of AEs leading to discontinuation (regardless of causality) were Grade 3 or 4 (reported in 11 of 53 subjects, 21%). Grade 3 events included lipase increased, ALT increased, AST increased, troponin I increased, colitis, diverticular perforation, pancreatitis, tachycardia, renal failure acute, choroiditis, autoimmune disorder, and pneumonitis. One subject each discontinued due to Grade 4 events of blood creatinine increased and AST increased. No drug-related deaths were reported.

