### **3.2.1.c General Treatment Instructions**

- As durable disease stabilization and/or objective tumor response can be seen after early progression before week 12, it is recommended that, in the absence of dose-limiting toxicities (eg, serious immune-mediated adverse reactions), all four doses of nivolumab plus ipilimumab be administered over the initial 12 weeks even in the setting of apparent clinical progression, providing the subject's performance status remains stable.
- All metastatic subjects who enter the induction period, including those who may have discontinued treatment for drug-related AEs and/or who have evidence of clinical progression during the induction period, should obtain a 12-week tumor assessment.
- Based on clinical experience in the ongoing and completed melanoma studies, the following recommendations apply for subject management in light of the week 12 or later tumor assessments:
  - The appearance of new lesions in subjects with other stable or shrinking baseline tumor burden may be experiencing clinical benefit and should continue in follow-up and/or maintenance therapy before alternative anti-cancer agents are considered. These subjects can be seen to have continued tumor shrinkage in follow-up scans.
  - As long as overall tumor burden is stable or decreasing, subjects should remain in follow-up and/or maintenance (see below), even in the presence of new lesions.
  - Clinical progression warranting alternative anti-cancer treatment should be considered only in subjects whose overall tumor burden appears to be substantially increased and/or in subjects whose performance status is decreased.

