### **3.4 Follow-up (duration of study)**

- Subjects who are no longer receiving treatment and are removed from the study because of unacceptable toxicity (refractory Grade > 3 immune-mediated adverse reactions) or due to investigator or his designee judgment are managed in follow-up. Efficacy assessments for these subjects during follow-up are as per the standard of care. Date of death is recorded.
- Subjects who discontinue treatments should be followed until death or the closure of the study (whichever is first).

- Subjects who are no longer receiving treatment because of clinical progression or who have switched to alternative treatment are not followed formally except to record the date of death.
- All subjects who come off study for any reason will be followed for at least 60 days, which is equal to 4 half-lives of the longest drug.

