## 6 STUDY PROCEDURES AND OBSERVATIONS

### 6.1 Time and Events Schedule

**Table 10: Time and Events Schedule for Protocol**

Procedure	Baseline a	Week 1, 4, 7, 10	Week 13 and every 4 weeks thereafter	Week 13 and every 12 weeks thereafter	End of Study
Eligibility					
Consent	X				
Inclusion/Exclusion	X				
Medical History	X				
Safety Assessments					
Interim History	X	X	X		X
Physical Examination	X	X	X		X
Vital signs, Height c , Weight, Performance Status	X c	X	X		X
Adverse Events	X	X	X b		X
Concomitant Medications	X	X	X		X
Common Laboratory Tests	X	X	X b		X

Liver Function Tests	X	X	X b		X
Thyroid Function Tests	X	X		X	X
Pregnancy Test e	X	X			
Tumor Measurementsc	X			X	
Correlative studies d		X	X		X
Nivolumab infusion		X	X b		
Ipilimumab infusion		X			

- a. Baseline visit and Week 1 visit may occur simultaneously.
- b. Patients will have adverse event assessments, common laboratory tests, liver function tests, and treatment every 4 weeks thereafter until removed from study.
- c. Tumor assessments will occur at baseline, Week 13 and every 12 weeks thereafter until removed from study. Assessments will have a window of +/- 7 days and will be in the form of CT chest, abdomen, pelvis with oral and intravenous contrast or acceptable alternative body imaging at the discretion of the investigator. Brain imaging only at the discretion of the investigator.
- d. Mandatory biopsy one-time during induction weeks 4-12, optional biopsy during maintenance and at the end of study
- e. Pregnancy test will be every 4 weeks during Maintenance phase (every other visit).

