## **9.1 Efficacy Analysis**

Study evaluations will take place in accordance with the flow charts in Section 5.1. Baseline assessments should be performed within 28 days prior to randomization utilizing CT or MRI. In addition to chest, abdomen, pelvis, and brain, all known sites of disease should be assessed at baseline. Subsequent assessments should include chest, abdomen, and pelvis, and all known sites of disease and should use the same imaging method as was used at baseline. Subjects will be evaluated for tumor response beginning 12 weeks (+/ 1 week) from randomization and continuing every 6 weeks ( $\pm$  1 week) for the first 12 months from randomization and every 12 weeks (+/ 1 week) thereafter, until disease progression is documented or treatment is discontinued (whichever occurs later). Tumor assessments for ongoing study treatment decisions will be completed by the investigator using RECIST (Response Evaluation Criteria in Solid Tumors) 1.1 criteria.

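### After a toxicity stop the plan gives conflicting rules on tumour assessment, so response may be under-ascertained and PFS censored at a non-random event

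*Combined protocol and SAP*

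**What the plan says.** Four places point towards protocol scans ending when a patient stops for toxicity:

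- Section 5.2.3 says that patients meeting its criteria must be taken off therapy and "withdrawn from the study for the following reasons". The list covers drug-related toxicities and also consent withdrawal, pregnancy, imprisonment and study termination.
- Synopsis, Criteria for Evaluation: "Efficacy will be evaluated at week 12 and then every 12 weeks until progression or treatment discontinuation".
- Table 10, footnote c: "Tumor assessments will occur at baseline, Week 13 and every 12 weeks thereafter until removed from study".
- Section 3.4, on patients removed for unacceptable toxicity: "Efficacy assessments for these subjects during follow-up are as per the standard of care". Date of death is still recorded.

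Two places point the other way:

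- Section 3.2.1.c: "All metastatic subjects who enter the induction period, including those who may have discontinued treatment for drug-related AEs", "should obtain a 12-week tumor assessment".
- Section 9.1 continues response evaluation "until disease progression is documented or treatment is discontinued (whichever occurs later").

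Section 6.4.3.e (irRC) counts every available assessment before subsequent therapy towards best response, and requires a second evaluation at least 4 weeks after response criteria are first met. Section 9 defines response as RECIST CR + PR and states no confirmation requirement. Section 9.2 names Kaplan-Meier for PFS but gives neither a PFS definition nor a censoring rule. Section 6.3.2 defines evaluability for safety; no section defines it for response.

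**The concern.** The primary endpoint is response rate, tested against a threshold of 4 responders in 27, so one or two unrecorded responses can change the conclusion. The regimen is expected to cause toxicity stops, and the protocol accepts that benefit can outlast treatment: Section 5.2.5 reports responses maintained in patients taken off ipilimumab, and Section 6.4.4 says immune activation may take weeks to months.

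If the synopsis, Section 5.2.3 and Table 10 are followed, a patient who stops for toxicity has at most the 12-week scan guaranteed by protocol. A later response, the irRC confirmatory evaluation and the progression date would then depend on whatever imaging routine care provides. The endpoint drifts towards response while still tolerating the drug, and PFS follow-up may end at an event that is plausibly related to prognosis.

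Because evaluability for response is undefined, the same patient could be counted as a non-responder or dropped from the 27, and that choice could be made after the outcome is known.

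**Working it through.** **1. The rules side by side, for a patient who stops for toxicity without progression**

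| Place | Protocol scans after the stop |
|---|---|
| Synopsis | None |
| 5.2.3 with Table 10, footnote c | None, since the patient is withdrawn |
| 3.4 | Standard of care, no fixed interval |
| 3.2.1.c | The 12-week scan, if the stop is in induction |
| 9.1 | Continue to documented progression |

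Section 5.2.3 keeps tumour assessments going during dosing interruptions, but says nothing similar for permanent discontinuation.

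**2. The plan's own figures (Section 9)**

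Inputs: n = 27, at least 4 responders, null 5%, alternative 20%.

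P(X ≥ 4 | p) = 1 − Σ C(27,k) p^k (1−p)^(27−k), summed over k = 0 to 3.

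- p = 0.05: 0.0437, the stated 4.4%.
- p = 0.20: 0.8177, so type II error is 0.1823, the stated 18.2%.
- Enrolment: 27/(1 − 0.30) = 38.6, so 39, as stated.

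**3. Illustration of possible loss**

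Let d be the share stopped for toxicity and m the share of their responses that is missed. Assume that response is independent of a toxicity stop and that missed responders stay among the 27 as non-responders. The observable rate is then 0.20 × (1 − d × m).

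The documents give no value for m. For d, the only figure for the combination is from the Phase 1 study in Section 1.3.6, where Grade 3 or 4 adverse events leading to discontinuation were "reported in 11 of 53 subjects, 21" per cent (11/53 = 0.208). At d = 0.21, 27 × 0.20 = 5.4 responders are expected, of whom 5.4 × 0.21 = 1.1 would be in the toxicity-stop group.

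| m | Observable rate, d = 21% | Power, d = 21% | Type I error, d = 21% | Power, d = 10% | Power, d = 40% |
|---|---|---|---|---|---|
| 0 | 20.0% | 81.8% | 4.4% | 81.8% | 81.8% |
| 25% | 0.20 × 0.9475 = 19.0% | 78.0% | 3.7% | 80.1% | 74.2% |
| 50% | 0.20 × 0.895 = 17.9% | 73.8% | 3.1% | 78.2% | 64.7% |
| 100% | 0.20 × 0.79 = 15.8% | 63.7% | 2.1% | 74.2% | 41.0% |

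The type I column applies the same factor to the null: 0.05 × (1 − d × m). A product d × m of 0.025 (10% × 25%) gives 80.1%, so about that much uses up the margin over 80%. At d = 21% this is 0.025/0.21, or about 12% of these patients' responses missed.

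**4. The other way of counting**

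If these patients are instead inevaluable and replaced until 27 evaluable patients are reached, and response is independent of toxicity, the 27 still respond at 20% and power stays at 81.8%.

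**The case against.** A reader might infer that all scanning stops at treatment discontinuation, that toxicity in induction prevents a response from being documented, and that PFS is informatively censored. The documents support none of these as fact.

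- Section 9.1, read literally, scans a patient who stopped for toxicity through to progression.
- Section 3.2.1.c keeps the 12-week scan, and Section 1.3.7.f says most responses to the combination came in the first 12 weeks. The exposure is therefore mainly to late responses and confirmation.
- Section 3.4 keeps these patients in follow-up, and Section 6.4.3.e lets routine scans count towards best response.
- The 4-week confirmation belongs to the irRC text; Section 9 sets no confirmation rule for RECIST response.
- No censoring rule is written, so informative censoring is a possibility that the plan leaves open.

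The 21% is also a weak proxy. It counts events regardless of causality, pools four dose cohorts, one of which exceeded the maximum tolerated dose, and comes from a longer dosing schedule. Its events include raised lipase, whereas Section 5.2.3 does not generally require stopping for Grade 3 laboratory abnormalities. Under non-responder counting, the error is conservative.

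All of this stands and limits the claim. It does not remove the conflict. Section 9.1 is contradicted by the synopsis and by the visit schedule, Section 3.2.1.c secures one scan only, and a rule that counts available scans does not ensure that any are taken.

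**Conclusion.** The rules on tumour assessment after a toxicity stop contradict each other and must be reconciled. If the synopsis, Section 5.2.3 and Table 10 prevail, response may be under-ascertained and PFS may be censored at a non-random event. If Section 9.1 prevails, little or nothing is lost.

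The size is not known. With 21% stopping, power is 78.0% to 63.7% as the share of their responses missed goes from 25% to 100%. This rests on a proxy rate, on response being independent of toxicity, and on counting missed responses as non-response. The 63.7% is an extreme case, because it requires every response in the group to be lost despite the 12-week scan and routine imaging; it should not be read as the trial's power. The harm under this counting is lost power, since type I error falls below 4.4%. Under replacement as inevaluable, power holds at 81.8% given independence, but the estimate then describes only patients whose response could be assessed. Leaving that choice open is itself a weakness.

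**What to change.** 1. In Section 5.2.3, separate stopping study therapy for adverse events from withdrawal from the study. Leave all toxicity stopping criteria, and the other listed reasons (consent withdrawal, pregnancy, imprisonment, study termination), unchanged.
2. Reconcile the synopsis, Section 3.4, Table 10 footnote c and Section 9.1. Patients who stop for toxicity without progression keep the protocol tumour assessments until progression, new anti-cancer therapy or death, unless imaging is contraindicated, for example by pregnancy (Sections 4.1 and 8.3.5 already make that exception).
3. In Section 9, state that treated patients who stop for toxicity stay in the response denominator.
4. In Section 9.2, define PFS events and the censoring rule, with a sensitivity analysis for patients whose scans end after a toxicity stop.
5. Section 9 records 23 evaluable patients already enrolled at the 2017 design change, so state how routine scans already taken after a toxicity stop will be used.

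The cost is amendment wording and some protocol-timed scans off drug, which Section 9.1 already provides for. No design number changes: with complete ascertainment, 4 of 27 keeps 4.4% type I error and 81.8% power.
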